2.5.2 Statistical hypothesis, model, and method of analysis

The primary efficacy analysis will be performed on the FAS. ORR will be summarized using descriptive statistics (N,%) along with 2-sided exact 95% confidence interval (CI) [Clopper and Pearson 1934].

Group 1: Well-differentiated NET

In the absence of historical comparator in this setting, response rates reported in placebo arms of previous randomized phase III studies in earlier lines of treatment can be considered as a valid historical reference for ORR (see Table 1-1 in the protocol). Based on it, the response rate for placebo is expected to be ca. 3% and it is desired to ensure that the observed response rate for PDR001 is significantly higher than expected placebo response rate. Furthermore, a response rate of 10% is considered clinically meaningful among patients with advanced NET of GI, pancreatic or thoracic origin.

Therefore, the results in this group will be considered a success if both of the following conditions are met:

1. a clinically relevant response rate of at least 10% is observed
2. the two-sided exact 95% CI excludes the value 3%.

With 90 patients in the FAS, these criteria correspond correspond to at least 9 responders observed (i.e. a response rate of 10% with 95% CI: [4.7; 18.1]).

Group 2: Poorly-differentiated GEP-NEC group

This group will enroll approximately 20 patients. Estimates of the ORR along with 95% two-sided CI will be presented. Additionally, the interval probabilities for the true ORR lying within the intervals stated below will be computed.

- 0 - <3% unacceptable efficacy
- 3% - <10% limited efficacy
- 10% - <20% moderate efficacy
- $\geq 20\%$ clinically relevant efficacy

For this analysis a prior distribution for the parameter of interest, ORR, must be specified. For the current study, the prior clinical assumption for PDR001 in the selected patient population is used in order to derive a minimally informative unimodal Beta prior distribution that reflects the level of uncertainty around ORR before starting the current trial (Neuenschwander et al 2008). The prior mean ORR is set to be equal to 15% and the parameters of the minimally informative Beta prior distribution of ORR have been set up as follows:

- $a/(a+b) = 0.15$
- $a = 0.176$

- $b = 1.0$

At the primary analysis, this prior distribution will be updated with observed ORR data and probabilities that the true ORR lies within the above intervals will be reported.

2.5.3 Handling of missing values/censoring/discontinuations

For the computation of ORR, all confirmed responses (CR or PR) reported up to the analysis cut-off will be included. Patients with no valid radiological assessment or unconfirmed responses will be considered as non-responders. In particular, patients with CR or PR at the last radiological assessment prior to cut-off and no response at the previous assessment are by definition unconfirmed and will be considered as non-responders for the primary analysis.

Patients with unknown or missing best overall response (BOR) will be counted as non-responders. If there is no baseline tumor assessment, all post-baseline overall lesion responses are expected to be 'Unknown'. If no valid post-baseline tumor assessments are available, the best overall response must be "Unknown" unless progression is reported. For the computation of ORR, these patients will be included in the FAS and will be counted as 'non-responders'.

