10.4.1 Variable

The primary efficacy variable of the study is overall response rate (ORR), defined as the proportion of patients with best overall response (BOR) of complete response (CR) or partial response (PR), as per blinded independent review committee. ORR will be evaluated according to RECIST 1.1 (see [Appendix 1](#) for details).

ORR will be calculated within each group based on the FAS and according to the ITT principle.

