10.4.3 Handling of missing values/censoring/discontinuations

For the computation of ORR, all confirmed responses (CR or PR) reported up to the analysis cut-off will be included. Patients with no valid radiological assessment or unconfirmed responses will be considered as non-responders. In particular, patients with CR or PR at the last radiological assessment prior to cut-off and no response at the previous assessment are by definition unconfirmed and will be considered as non-responders for the primary analysis.

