2.5 Evaluation of overall lesion response

The evaluation of overall lesion response at each assessment is a composite of the target lesion response, non-target lesion response and presence of new lesions as shown below in [Table 2-3](#).

Table 2-3 Overall lesion response at each assessment

Target lesions	Non-target lesions	New Lesions	Overall lesion response
CR	CR	No	CR ¹
CR	Non-CR/Non-PD ³	No	PR
CR, PR, SD	UNK	No	UNK
PR	Non-PD and not UNK	No	PR ¹
SD	Non-PD and not UNK	No	SD ^{1, 2}
UNK	Non-PD or UNK	No	UNK ¹
PD	Any	Yes or No	PD
Any	PD	Yes or No	PD
Any	Any	Yes	PD

^{1.} This overall lesion response also applies when there are no non-target lesions identified at baseline.

^{2.} Once confirmed PR was achieved, all these assessments are considered PR.

^{3.} As defined in [Section 2.4](#).

If there are no baseline scans available at all, then the overall lesion response at each assessment should be considered Unknown (UNK).

In some circumstances it may be difficult to distinguish residual disease from normal tissue. When the evaluation of complete response depends on this determination, it is recommended that the residual lesion be investigated (fine needle aspirate/biopsy) to confirm the CR.

3 Efficacy definitions

The following definitions primarily relate to patients who have measurable disease at baseline. [Section 3.2.8](#) outlines the special considerations that need to be given to patients with no measurable disease at baseline in order to apply the same concepts.

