- PR = at least two determinations of PR or better at least 4 weeks apart before progression (and not qualifying for a CR) where confirmation required or one determination of PR prior to progression where confirmation not required
- SD = at least one SD assessment (or better) > 6 weeks after randomization/start of treatment (and not qualifying for CR or PR).
- PD = progression \leq 12 weeks after randomization/ start of treatment (and not qualifying for CR, PR or SD).
- UNK = all other cases (i.e. not qualifying for confirmed CR or PR and without SD after more than 6 weeks or early progression within the first 12 weeks)

The time durations specified in the SD/PD/UNK definitions above are defaults based on a 6 week tumor assessment frequency. However these may be modified for specific indications which are more or less aggressive. In addition, it is envisaged that the time duration may also take into account assessment windows. E.g. if the assessment occurs every 6 weeks with a time window of +/- 7 days, a BOR of SD would require a SD or better response longer than 5 weeks after randomization/start of treatment.

Overall lesion responses of CR must stay the same until progression sets in, with the exception of a UNK status. A patient who had a CR cannot subsequently have a lower status other than a PD, e.g. PR or SD, as this would imply a progression based on one or more lesions reappearing, in which case the status would become a PD.

Once an overall lesion response of PR is observed (which may have to be a confirmed PR depending on the study) this assignment must stay the same or improve over time until progression sets in, with the exception of an UNK status. However, in studies where confirmation of response is required, if a patient has a single PR ($\geq 30\%$ reduction of tumor burden compared to baseline) at one assessment, followed by a $< 30\%$ reduction from baseline at the next assessment (but not $\geq 20\%$ increase from previous smallest sum), the objective status at that assessment should be SD. Once a confirmed PR was seen, the overall lesion response should be considered PR (or UNK) until progression is documented or the lesions totally

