disappear in which case a CR assignment is applicable. In studies where confirmation of response is not required after a single PR the overall lesion response should still be considered PR (or UNK) until progression is documented or the lesion totally disappears in which case a CR assignment is applicable.

Example: In a case where confirmation of response is required the sum of lesion diameters is 200 mm at baseline and then 140 mm - 150 mm - 140 mm - 160 mm - 160 mm at the subsequent visits. Assuming that non-target lesions did not progress, the overall lesion response would be PR - SD - PR - PR - PR. The second assessment with 140 mm confirms the PR for this patient. All subsequent assessments are considered PR even if tumor measurements decrease only by 20% compared to baseline (200 mm to 160 mm) at the following assessments.

If the patient progressed but continues study treatment, further assessments are not considered for the determination of best overall response.

Note: these cases may be described as a separate finding in the CSR but not included in the overall response or disease control rates.

The best overall response for a patient is always calculated, based on the sequence of overall lesion responses. However, the overall lesion response at a given assessment may be provided from different sources:

- Investigator overall lesion response
- Central Blinded Review overall lesion response
- Novartis calculated overall lesion response (based on measurements from either Investigator or Central Review)

The primary analysis of the best overall response will be based on the sequence of investigator/central blinded review/calculated (investigator)/calculated (central) overall lesion responses.

Based on the patients' best overall response during the study, the following rates are then calculated:

Overall response rate (ORR) is the proportion of patients with a best overall response of CR or PR. This is also referred to as 'Objective response rate' in some protocols or publications.

Disease control rate (DCR) is the proportion of patients with a best overall response of CR or PR or SD. The objective of this endpoint is to summarize patients with signs of "activity" defined as either shrinkage of tumor (regardless of duration) or slowing down of tumor growth.

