2.5.1 Primary endpoint

ORR is defined as the proportion of patients with best overall response (BOR) of complete response (CR) or partial response (PR) according to RECIST 1.1 (see Appendix 1 of the study protocol). ORR will be calculated within each group based on the FAS using BIRC review of tumor assessment data. Patients with only non-measurable disease at baseline will be part of the analysis and will be included in the numerator only if a complete response was observed. Tumor assessments performed before the start of any further antineoplastic therapy (i.e. any additional secondary antineoplastic therapy or surgery) will be considered in the assessment of BOR. Limited-field palliative radiotherapy administered as concomitant therapy per protocol will not

be considered as new antineoplastic therapy. Localized radiotherapy and treatment with bisphosphonates for pre-existing, painful bone/liver metastases is permitted.

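### Read literally, the last-scan sentence in SAP 2.5.3 and Protocol 10.4.3 makes PR-SD-PR a non-response, while Appendix 1, which defines the primary ORR, counts it as a confirmed PR

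*SAP*

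**What the plan says.** Protocol 10.4.1 defines the primary variable by reference: "ORR will be evaluated according to RECIST 1.1", with Appendix 1 for details. SAP 2.5.1 makes the same reference.

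Appendix 1, section 3.1, sets the confirmation rule. A best overall response of PR needs "at least two determinations of PR or better at least 4 weeks apart before progression". It does not ask for adjacent scans. Its worked example starts from 200 mm and runs 140, 150, 140, 160, 160 mm, read as PR-SD-PR-PR-PR. On the third scan it says: "The second assessment with 140 mm confirms the PR for this patient".

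SAP 2.5.3 and Protocol 10.4.3 first include every confirmed response up to cut-off and class unconfirmed responses as non-responses. A sentence opening *In particular* follows: "patients with CR or PR at the last radiological assessment prior to cut-off and no response at the previous assessment are by definition unconfirmed". The protocol version ends that such patients "are by definition unconfirmed and will be considered as non-responders for the primary analysis".

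**The concern.** The last-scan sentence looks only at the scan immediately before the last one. It does not ask whether there was a qualifying response earlier still. A patient with PR-SD-PR ending at the last scan before cut-off has no response at the previous assessment, so the sentence makes that patient a non-responder. Appendix 1 makes the same patient a confirmed responder.

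What depends on this is responder status on the primary endpoint in both groups. The well-differentiated group has a hard threshold (observed ORR of at least 10%), and the ORR subgroup summaries are produced only if the success criteria are met (SAP 2.2.1 and 2.5.4). The key secondary endpoint, duration of response, is summarised for confirmed responders only (Protocol 10.5.1, SAP 2.6.2), so it inherits the ambiguity.

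**Working it through.** **1. The plan's own figures.** 9/90 = 10.0%, exact 95% CI 4.68 to 18.14%; the plan states 4.7 to 18.1. P(X ≥ 9) for Bin(90, p) is 0.551 at p = 10% and 0.937 at p = 15%; the plan states 0.55 and 0.94. All reproduce.

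**2. The Appendix 1 example.** From 200 mm:
- 140 mm is −30%: PR.
- 150 mm is −25%, and 10/140 = +7.1% above the smallest sum: SD, not PD.
- 140 mm is −30%: PR, stated to confirm.

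With scans every 8 weeks, two PRs with one scan between them are about 16 weeks apart, well over the 4-week minimum.

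**3. The two rules side by side**, for sequences ending at the last scan before cut-off:

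| Sequence | Appendix 1 | Last-scan sentence, literal |
|---|---|---|
| SD-PR | non-responder | non-responder |
| PR-PR | responder | responder |
| PR-SD-PR-PR | responder | responder |
| PR-PR-SD-PR | responder | responder |
| PR-SD-PR | responder | **non-responder** |
| PR-UNK-PR | responder | **non-responder**, if UNK is no response |
| PR-PR-UNK-PR | responder | **non-responder**, if UNK is no response |

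PR-PR-SD-PR is safe because an SD after a confirmed PR is itself read as PR (Appendix 1, Table 2-3, footnote 2: "Once confirmed PR was achieved, all these assessments are considered PR"). An UNK is not carried forward in that way, which is why the already confirmed PR-PR-UNK-PR is caught. Among all 27 three-scan sequences of PR, SD and UNK, the rules disagree in exactly two: PR-SD-PR and PR-UNK-PR.

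**4. Size, well-differentiated group.** Protocol 1.2.1.2 gives a full analysis set of 95. One patient is worth 1/95 = 1.05 percentage points.

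| Responders of 95 | ORR | Exact 95% CI | Success |
|---|---|---|---|
| 7 (last reported) | 7.37% | 3.01 to 14.59 | no |
| 9 | 9.47% | 4.42 to 17.22 | no (below 10%) |
| 10 | 10.53% | 5.16 to 18.51 | yes |

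So one disputed patient matters for the verdict only when the undisputed count is exactly 9. P(X = 9) for Bin(95, p) is 0.105 at p = 7.4%, 0.136 at 10% and 0.038 at 15%. This must be multiplied by the chance that a patient shows the pattern at cut-off, which the documents do not give. Assuming 1% to 20%, independent of the undisputed count:
- p = 7.4%: 0.105 × 0.01 to 0.20 = 0.1% to 2.1%
- p = 10%: 0.136 × 0.01 to 0.20 = 0.1% to 2.7%
- p = 15%: 0.038 × 0.01 to 0.20 = 0.04% to 0.8%

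**5. Size, GEP-NEC group.** The posterior is Beta(0.176 + x, 1 + n − x). With n = 20, P(ORR ≥ 10%) is 15.8% for x = 1 and 44.0% for x = 2, as in Protocol Table 10-4. With the actual n = 21, it is 14.3% and 41.2%. One responder was last reported, so one disputed patient would be the difference between 1/21 = 4.8% and 2/21 = 9.5%.

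**The case against.** The strongest reply is that the paragraph can be read consistently. Its first sentence includes all confirmed responses. *In particular* then only illustrates the unconfirmed ones, and the appeal to definition can only mean Appendix 1, under which PR-SD-PR is confirmed. The optional sensitivity analysis in SAP 2.5.4 also describes unconfirmed cases as responses at the last scan in patients still in efficacy follow-up, that is, awaiting confirmation. This is the likely intent, and it makes the point minor.

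It does not remove the point, because nothing in the sentence limits it to patients without an earlier response. For irRECIST, SAP 2.7.1 says outright that the two irPR assessments need not be consecutive; the primary endpoint has no such statement, and a programmer could take the difference as deliberate. The SAP 2.5.4 analysis does not settle it either: it is optional, and it would pool these patients with true first responses at the last scan.

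A reader might infer that PR-UNK-PR is as plain a contradiction as PR-SD-PR. The documents do not support that. Appendix 1 has no explicit sentence on confirmation across UNK (only irRECIST, in Appendix 2, has one), and the conflict depends on treating UNK as no response.

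The objection that the size rests on assumptions also stands. The 1% to 20% range has no source in the documents, and the binomial calculation ignores that 7 responders had already been reported. The GEP-NEC group has no success criterion, so its posterior shift is a change in a descriptive output.

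**Conclusion.** The literal conflict is real and firm for PR-SD-PR, since Appendix 1 uses that very sequence as its example of confirmation. It extends to PR-UNK-PR and PR-PR-UNK-PR only if UNK is read as no response. It is a minor wording error in a primary-endpoint rule.

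A reader might infer that the reported ORR is biased or that the success verdict is at risk. The documents do not show this: no patient is known to have the pattern, and its frequency is unknown. The error can only lower ORR, so it cannot create a false success. With one disputed patient the well-differentiated verdict turns only at exactly 9 undisputed responders of 95; under the stated assumptions the chance is at most 2.7%.

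A reader might also infer that consecutive confirmation was intended. SAP section 4 lists one change to the protocol-specified analyses, and this is not it.

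**What to change.** In SAP 2.5.3, before database lock, replace the *In particular* sentence with:

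> *A CR/PR at the last assessment before cut-off is unconfirmed if there is no earlier CR/PR at least 4 weeks before it among the assessments eligible for BOR (before PD and before any further antineoplastic therapy, SAP 2.5.1). Confirmation follows Appendix 1 section 3.1: an intervening SD (for PR) or UNK does not prevent confirmation, and a BOR of CR needs two CRs.*

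Both eligibility limits are needed. Treatment and scans may continue after RECIST progression (Protocol 6.1.5.1), but Appendix 1 says: "If the patient progressed but continues study treatment, further assessments are not considered for the determination of best overall response". Scans also continue after new antineoplastic therapy starts (Protocol 4.1.1, 7.1.5 and 7.1.8), while SAP 2.5.1 uses only those before it. Without these limits the new wording could wrongly add responders.

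If consecutive confirmation is what the sponsor wants, state it in SAP section 4 as a departure from Appendix 1.

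Cost: a short SAP edit and no new data. Protocol 10.4.3 needs the same text, but Protocol 12.1 requires a formally approved amendment for any change, so that can wait for the next one.

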2.5.4 Supportive analyses

A sensitivity analysis considering patients with unconfirmed PR or CR (i.e. with PR or CR at the last assessment prior to the cutoff and ongoing in efficacy follow-up) as responders may be performed if large delayed treatment effect is observed.

The analysis of ORR will be repeated based on local review.

Concordance analysis of BOR

An assessment of the concordance between BIRC assessment and local assessment of the Best Overall Response for each subject will be provided. The calculation will be based on the percent agreement (the proportion of response outcomes that agree or match across both Independent Reviewer and Investigator Assessments):

Percent Agreement = (Number of matched responders + Number of matched non-responders) / total number of subjects assessed.

Subgroup analyses for the primary endpoint

If both criteria for the primary efficacy analysis are met, the primary endpoint of ORR will be summarized for the subgroups specified in [Section 2.2.1](#) based on the primary analysis source (i.e. BIRC) and the same conventions as for the primary analysis.

For each of the subgroups, the following analyses will be performed:

- Proportion of patients with objective response
- two-sided exact 95% CI

Efficacy analyses in subgroups will be purely exploratory and are intended to explore the consistency of treatment effect.

Reasons for “Unknown” BOR

Patients with ‘unknown’ BOR will be summarized by reason for having unknown status. The following reasons will be used:

- No valid post-baseline assessment
- All post-baseline assessments have overall lesion response UNK
- New anti-neoplastic therapy started before first post-baseline assessment
- SD or non-CR/non-PD too early
- PD too late

Note 1: A SD or Non-CR/Non-PD is considered as “SD too early” if the SD or Non-CR/Non-PD is documented within first 6 weeks after treatment start date.

Note 2: A PD is considered as “PD too late” if the first documentation of PD is recorded more than 12 weeks after treatment start date with no qualifying CR, PR or SD or Non-CR/Non-PD in between.

Note 3: Special (and rare) cases where BOR is “unknown” due to both too early SD and too late PD will be classified as “SD too early”.

Waterfall plot to depict anti-tumor activity

Waterfall graphs will be used to depict the anti-tumor activity. These plots will display the best percentage change from baseline in the sum of diameters of all target lesions for each patient. Only patients with measurable disease at baseline will be included in the waterfall graphs. Special consideration is needed for assessments where the target lesion response is CR, PR or SD, but the appearance of a new lesion or a worsening of non-target lesions results in an overall lesion response of PD. As a conservative approach, such assessments will not be considered for display as bars in the graph, since the percentage change in the sum of diameters of target lesions reflects the non-PD target lesion response, but the overall lesion response is PD. A patient with only such assessments will be represented by a special symbol (e.g. □) in the waterfall graph. Assessments with “unknown” target lesion response and assessments with unknown overall response will be excluded from the waterfall plots. Patients without any valid assessments will be completely excluded from the graphs.

The total number of patients displayed in the graph will be shown and this number will be used as the denominator for calculating the percentages of patients with tumor shrinkage and tumor growth. Footnote will explain the reason for excluding some patients (due to absence of any valid assessment).

All possible assessment scenarios are described in [Table 2-4](#).

Table 2-3 Inclusion/exclusion of assessments used in waterfall graph

	Criteria for inclusion/exclusion			Possible sources of contradictions	
case	Target response	Overall lesion response	Include in waterfall?	Non-target response	New lesion?

1	CR/PR/SD	PD	Yes but as ' only	PD	any
2	CR/PR/SD	PD	Yes but as ' only	any	Yes
3	UNK	UNK or PD	No	any	any
4	CR/PR/SD	UNK	No	UNK	No
5	CR/PR/SD	CR/PR/SD	Yes as a bar	SD/IR	No
6	PD	PD	Yes as a bar	any	any

Percentage change from baseline in the sum of diameters of all target lesions over the time will be displayed for individual patients.

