7.2.3 Post-baseline imaging assessments

Imaging assessments as described in [Table 7-2](#) should be performed using the same imaging modality used at baseline, irrespective of study treatment interruption or actual dosing (see [Table 7-1](#)).

Prior to the primary analysis cut-off date (10-Aug-2018), imaging assessments for response evaluation will be performed every 8 weeks (+/- 7 days) until Cycle 13, and every 12 weeks (+/- 7 days) thereafter until disease progression per RECIST 1.1 or irRECIST per BIRC, death, lost to follow-up or withdrawal of consent. Imaging assessments should be scheduled using the date of first dose (Cycle 1 Day 1) as the reference date (not the date of the previous tumor assessment), and should be respected regardless of whether treatment with study treatment is temporarily withheld or unscheduled assessments performed.

Additional imaging assessments may be performed at any time during the study at the investigator's discretion to support the efficacy evaluations for a patient, as necessary. Clinical suspicion of disease progression at any time requires a physical examination and imaging assessments to be performed promptly rather than waiting for the next scheduled imaging assessment.

Each lesion that is measured at baseline must be measured by the same method (either same imaging method or by photography, including a metric ruler) and when possible, the same local

radiologist/physician throughout the study so that the comparison is consistent. If an off-schedule imaging assessment is performed because progression is suspected, subsequent imaging assessments should be performed in accordance with the original imaging schedule.

Combined PET/CT may be used only if the CT is of similar diagnostic quality as a CT performed without PET, including the utilization of IV contrast media. At the discretion of the Investigators, FDG-PET scans may be performed to document progressive disease per RECIST 1.1 ([Appendix 1](#)) or per irRECIST ([Appendix 2](#)).

All study imaging (including any off-schedule imaging studies) should be submitted to the designated imaging CRO for quality control and central review.

After the primary analysis cut-off date (10-Aug-2018):

- For patients on study treatment, imaging assessments will be scheduled according to local or institutional standard of care, as clinically indicated, and will continue until study treatment discontinuation.

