2.7.3 Handling of missing values/censoring/discontinuations

If a patient is not known to have died at the time of analysis cut-off, then OS will be censored at the date of last known date patient was alive, i.e., last contact date.

The date of last adequate tumor assessment is the date of the last tumor assessment with overall lesion response of CR, PR or SD or non-CR/non-PD before an event or a censoring reason occurred. In this case the last tumor evaluation date at that assessment will be used. If no post-baseline assessments are available (before an event or a censoring reason occurred) then the start date of treatment will be used.

In particular, PFS will be censored at the last adequate tumor assessment if one of the following occurs: absence of event; the event occurred after two or more missing tumor assessments. The term “missing adequate tumor assessment” is defined as a tumor assessment not performed or tumor assessment with overall lesion response of “UNK”. The rule to determine number of missing TAs is based on the time interval between the date of last adequate tumor assessment and the date of an event. If the interval is greater than twice the protocol-specified interval between the TAs and 2 times the protocol-allowed time window around assessments, then the number of missing assessments will be 2 or more.

As per protocol, tumor assessments are expected to be performed every 8 weeks for the first 12 months and every 12 weeks thereafter.

Therefore:

- if the last adequate tumor assessment is performed before end of week 36 (i.e. from study day 1 to study day $36*7=252$) then the interval of 2 missing tumor assessments is given as $2*8+2=18$ weeks (126 days);
- if the last adequate tumor assessment is performed from end of week 36 up to end of week 44 (i.e. from study day 253 to study day $44*7=308$) then the interval of 2 missing tumor assessments is given as $8+12+2=22$ weeks (154 days);
- otherwise, when the last adequate tumor assessment is performed after end of week 44 (i.e. from study day $44*7+1=309$ onward), then the interval of 2 missing tumor assessments is given as $2*12+2=26$ weeks (182 days).

These summaries on censoring reasons will be produced for PFS by investigator and BIRC.

Refer to [Table 2-5](#) for censoring and event date options and outcomes for PFS.

Table 2-4 Outcome and event/censor date for PFS analysis

Situation	Date	Outcome
No baseline assessment	Date of start of treatment	Censored

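### The 12-week limit for a best response of PD was not adapted to the 8-week scan schedule, so PD at the second scheduled scan after a missed or UNK first scan is always reported as Unknown

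*SAP*

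**What the plan says.** Protocol Appendix 1, section 3.1, assigns a best response of PD when progression occurs no later than 12 weeks after start of treatment and the patient does not qualify for CR, PR or SD. Cases that fit no category become UNK. The same section adds: "The time durations specified in the SD/PD/UNK definitions above are defaults based on a 6 week tumor assessment frequency". It allows them to be changed for more or less aggressive indications, and "it is envisaged that the time duration may also take into account assessment windows".

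The schedule here is different. Protocol 7.2.3 states that "imaging assessments for response evaluation will be performed every 8 weeks (+/- 7 days) until Cycle 13", counted from the first dose. SAP 2.7.3 recognises this: "tumor assessments are expected to be performed every 8 weeks for the first 12 months and every 12 weeks thereafter".

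The protocol body does not adapt the BOR limits, and SAP 2.5.4 restates both defaults. Under Note 1, stable disease is too early "if the SD or Non-CR/Non-PD is documented within first 6 weeks after treatment start date". Under Note 2, progression is too late when "the first documentation of PD is recorded more than 12 weeks after treatment start date with no qualifying CR, PR or SD" comes in between. 'PD too late' is one of the listed reasons for an Unknown BOR. For irRECIST, Protocol Appendix 2, section 4.3, carries the same 12-week limit for irPD.

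**The concern.** The limit decides whether a documented progressor appears in the BOR summary as PD or as Unknown. On an 8-week schedule, 12 weeks falls between the first and second scheduled scans, so a patient whose first scan is unusable has no scheduled opportunity left to be classified as PD.

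Such records are plausible. Under Appendix 1, sections 2.2 and 2.5, a change in contrast use or imaging technique, or lesions that were not assessed, leads by default to an UNK response.

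The SAP did adapt its PFS rule for missing assessments to the 8-week interval. The same central-review record can therefore be a dated progression in the PFS analysis and an Unknown best response in the table beside the primary endpoint. A reader of that table would see fewer progressors and more patients without a determinable response than the scans show.

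**Working it through.** **Inputs.** PD limit: 12 weeks = 12 x 7 = 84 days (SAP 2.5.4 Note 2; Appendix 1, 3.1). Scan interval: 8 weeks = 56 days, window 7 days either side, counted from first dose (Protocol 7.2.3). PFS interval for two missing assessments early in the study: 2 x 8 + 2 = 18 weeks = 126 days (SAP 2.7.3).

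**Scheduled scans in this trial, in days after start of treatment.**
- First scan: 56 - 7 = 49 to 56 + 7 = 63.
- Second scan: 112 - 7 = 105 to 112 + 7 = 119.

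The 84-day limit lies after every permitted first scan and 105 - 84 = 21 days before the earliest permitted second scan.

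**Record tested:** first scan missed or UNK, no other scan, PD at the second scheduled scan. The 6-week row uses the same 7-day window for comparison.

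| Schedule | Second scan (earliest / nominal / latest) | Limit | BOR |
|---|---|---|---|
| 6-week | 77 / 84 / 91 days | 84 days | PD / PD / Unknown |
| 8-week | 105 / 112 / 119 days | 84 days | Unknown / Unknown / Unknown |
| 8-week | 105 / 112 / 119 days | 112 days | PD / PD / Unknown |
| 8-week | 105 / 112 / 119 days | 119 days | PD / PD / PD |

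On the schedule for which the default was written, the nominal second scan gives PD. On this trial's schedule no in-window second scan does.

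**The same record under the PFS rule.** With no adequate post-baseline assessment, the interval runs from start of treatment. Its length is 105 to 119 days, which does not exceed 126, so fewer than two assessments count as missing. The SAP 2.7.3 table then gives progression on its own date.

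**What else moves.**
- ORR: PD and Unknown are both non-responders (SAP 2.5.3), so neither ORR nor the success criterion changes.
- Concordance of BOR: SAP 2.5.4 computes it on responders versus non-responders, so it does not change.
- DCR: it counts CR, PR and SD only.
- DoR: it concerns responders only.

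**The case against.** **The default is permitted.** Appendix 1 allows modification and does not require it, and the SAP states its rule explicitly. This stands: the rule is pre-specified and can be applied as written. The criticism is that it does not fit the schedule.

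**Unknown may be the honest label.** If the week-8 scan is unusable, the patient may have had stable disease then, so the best response is in a sense not known. This also has force, and it is why calling these patients misclassified would go too far. However, Appendix 1 accepts the same uncertainty on a 6-week schedule, where an unusable first scan followed by PD at day 84 gives PD.

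**The patients are already visible.** The 'PD too late' row separates them from patients who could not be evaluated, and a reader can add them back. This stands and limits the harm.

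**The case is narrow.** Central reviewers may replace UNK after a change of method (Appendix 1, 2.2 and 2.4.2), and suspected progression calls for prompt imaging (Protocol 7.2.3), so some patients would have PD documented by day 84. That reduces the number but does not change the rule for those who remain.

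**One possible rescue does not clearly apply.** SAP 2.5.3 makes an exception where progression is reported, but only for patients with no valid post-baseline assessment. Here the second scan is a valid assessment.

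A reader might also infer three stronger points that the documents do not support:
- That the 6-week SD limit is equally wrong and inflates DCR. The earliest in-window scan is at 49 days, beyond 42, so no in-window scan is affected. A rule of more than 7 weeks could reject a permitted scan at exactly 49 days.
- That Appendix 1 defines 12 weeks as two scans. The match with 2 x 6 is an inference; the text only ties the limit to a 6-week frequency. On that schedule PD on days 85 to 91 would also be Unknown.
- That a patient count can be given. Any figure would need assumed rates of unusable first scans and of later PD, and the documents contain neither.

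**Conclusion.** The point holds as a minor one. The 12-week limit for BOR PD, and for irPD, is tied by the protocol's own appendix to a different scan frequency. As written, it always turns PD at the second scheduled scan into Unknown when the first scan is missed or UNK. This assumes no qualifying SD or better in between and no unscheduled scan showing PD by day 84.

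The effect is confined to the PD versus Unknown split in the BOR summary and its irRECIST counterpart. The number of patients is not derivable. Each RECIST reclassification is 1/21 = 4.8 percentage points of the GEP-NEC group or 1/95 = 1.1 points of the well-differentiated group, using the group sizes in Protocol 1.2.1.2. No efficacy conclusion depends on it.

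**What to change.** In SAP 2.5.4, state a study-specific limit: BOR is PD if the first documented progression occurs within 17 weeks, that is up to and including 119 days after start of treatment (2 x 56 + 7 = 119), with no qualifying CR, PR or SD. Redefine 'PD too late' as later than that. Apply the same limit to irPD in place of the 12 weeks in Appendix 2, section 4.3. Give the limit in days: under the SAP 2.1.1 convention, 119 days after start is study day 120. A 16-week limit without the window would still leave a permitted scan at day 119 as Unknown. Leave the 6-week SD limit unchanged.

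This brings BOR close to the PFS rule. PD at the third scheduled scan (168 - 7 = 161 to 168 + 7 = 175 days) after two unusable scans would stay Unknown, and PFS would censor it because 161 exceeds 126. PD on days 120 to 126, outside the scan window, would remain a PFS event with an Unknown BOR.

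The cost is a few lines of SAP text and one constant each in the RECIST and irRECIST BOR derivations. The downside is that a few patients move from Unknown to PD. If the default is kept, the SAP should say why, and the table should carry a footnote that 'PD too late' patients have documented progression.
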